coordinator's phone number in case they require additional information or want to discuss aspects of the study, as well as to indicate interest in the study. For those who did not respond to the letter within two weeks of mailing, the study coordinator will contact them over the phone to explain the study and determine interest in participating. For all those interested in participating, the study coordinator will arrange a date and time to meet in the clinic. Details of the study and the consent form will be reviewed in-person at this time to ensure that patients are fully informed about all aspects of the study and are freely providing their consent to participate.

To perform a sample size calculation, the primary outcome measure SF-36 was used. Assuming a moderate effect size on the general health dimension of the SF-36 of 10.5 points (39), a score of 57 +/- 21 for the control group (40), 80% power, and alpha=0.05 (two-sided), the sample size per group was calculated to be 63 (<http://clincalc.com/Stats/SampleSize.aspx>). Assuming 15% of patients will be lost to follow-up (including mortality) (36, 37), the sample size per group is 73. Hence 146 patients will be enrolled during the trial and randomized 1:1 into control and telemonitoring groups.

To perform the randomization, the online computer generated randomization tool, Research Randomizer, will be used ([www.randomizer.org](http://www.randomizer.org)). The study coordinator performing the recruitment will be blinded until the patient has consented to participate. The participants will be blocked randomized (blocks of 4) and stratified into groups according to their primary condition (HF, COPD, hypertension, insulin-requiring diabetes, and CKD). The HF group will further be stratified based on NYHA classification (NYHA class 2-3, NYHA class 4), and the hypertensive patients will be stratified to those with and those without diabetes.

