## **Outcome Measures:**

The primary outcome will be health status as measured with SF-36 because this metric will be relevant to all chronic conditions under investigation. A secondary

outcome measure will be the cost (from the health system and patient perspectives). The cost of healthcare will include hospitalizations, emergency department (ED) visits, clinic visits, delay of hemodialysis commencement, medications, and telemonitoring program, as relevant to the different chronic illnesses and will include disease-specific sub-analyses.

Other secondary outcome measures will include combined hospitalization for any reason or death from any cause within 6-months after enrolment, hospitalization, mortality, days in hospital, number of emergency department (ED) and clinic visits, and medications. Secondary outcome measures will also include general quality of life as measure by the EuroQol 5D-RL, anxiety and depression as measure with the Hospital Anxiety and Depression Scale (41) and patients' self-efficacy to self-manage their disease as measured with the Self-Efficacy for Managing Chronic Disease Scale (42) (Appendix 3).

Disease specific outcome measures will include:

- HF
  - left ventricular ejection fraction (LVEF)
  - brain natriuretic peptide (BNP)
  - self-care as measured by the Self-Care of Heart Failure Index (43) (Appendix 4)
  - Heart-failure specific quality of life as measured by Minnesota Living with Heart Failure Questionnaire (44) (Appendix 4)
  - Shortness of breath as measure using a visual analogue scale (VAS) for dyspnea (Appendix 4)
  - Blood work: creatinine, sodium, potassium, hemoglobin, urate
  - Prognostic score as determined by the Seattle Health Failure Model (requires: age, gender, NYHA class, weight, ejection fraction, systolic BP, medication list (including diuretics), lab results (hemoglobin, lymphocytes, uric acid, total cholesterol, sodium) and QRS interval)
- COPD
  - forced expiratory volume in one second (FEV1)
  - symptoms score from the telemonitoring system
  - COPD Assessment Test (CAT) score (45) (Appendix 5)
  - COPD-specific knowledge after 6-months of application usage, as measured by the Bristol COPD Knowledge Questionnaire (BCKQ)(46) (Appendix 5)
  - patient self-efficacy at 6 months as measured by the COPD Self-Efficacy Scale (CSES)(47) (Appendix 5)
  - COPD severity as measured by the BODE Index(48) at 6 months (Appendix 5)

- CKD
  - estimated glomerular filtration rate (eGFR)

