  - symptoms score from the telemonitoring system
  - blood pressure as measured by an automatic blood pressure monitor
- Hypertension
  - blood pressure as measured by an automatic blood pressure monitor
  - average 7-day blood pressure
- Diabetes
  - HgbA1c

**Data Acquisition:** Number of hospitalizations, days in hospital, number of ED and clinic visits, and medications will be determined through the hospital EMR and a manual chart review of all participants' clinical records. Combined hospitalization will be verified by patient participants through self-report with the help of a questionnaire. The cost of the intervention will be tracked, including for equipment costs and human resources for clinical support, technical support, and program management. Standard cost values for a day in-hospital, ED visit, etc. will be used to estimate net cost savings or expenditures. Values for pre- and post-trial health outcome measures (eg, blood test results) will be obtained through hospital clinical records or through the *Medly* database for symptoms. Pre- and follow up questionnaires (baseline, 1-month, and 6-months), will be administered to both control and intervention groups that contain the validated survey tools listed above. Participants will be able to complete the questionnaires at the clinic or complete it at home. Participants that chose to complete the questionnaire at home will be given a pre-paid self-addressed envelope to mail the questionnaire back to the study team. The 1-month questionnaire will be given to participants upon enrolment with instructions to complete the questionnaire one month after starting the trial and to mail it back to the study team using the pre-paid envelope. The study coordinator will call each participant at the 1-month period to remind participants to complete the questionnaire. In addition to the baseline and follow up questionnaires that are applicable to all patient participants (Appendix 3), patients with HF and/or COPD will also receive the validated survey tools listed above (Appendix 4 and 5). Average 7-day blood pressure will also be recorded from patients with a primary diagnosis of hypertension during their first week in the study (baseline) and their last week in the study (6-months). To do this, patients will be provided with a digital blood pressure monitor which they will use to take blood pressure 4 times per day (2 times in the morning and 2 times in the evening) over each 7-day period. Patients will return the blood pressure monitor to the study team who will download the

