**Data Analysis:** Post-trial data and change scores will be compared between the control and intervention groups using independent Student t tests and Mann-Whitney tests (for normally and not normally distributed data, respectively). Paired Student t tests and Wilcoxon signed rank tests will be performed to compare baseline and post-study data within the control and telemonitoring groups. The statistical analyses will be performed using the statistical software application SPSS (IBM Corporation, USA). The cost evaluation will be performed by comparing any savings through reductions in hospitalization, emergency and clinic visits, through the use of the intervention. This will further include amortizing the equipment costs and factoring in additional clinical, technical, and management resources. An analysis of indirect costs will also be performed, such as days absent from work. Interview data will be analyzed using a conventional content analysis approach (49). Two researchers will analyze the transcripts independently and code the transcripts with the software program NVivo (QSR International, Doncaster, Victoria, Australia).

The Principle Investigator will keep all study data in a secure and confidential location for 10 years after the completion of the study and then they will destroyed by shredding of paper or erasing of digital information. All participants will be assigned a unique identifier, which will replace any identifiable information contained in the research data. A list linking the study number with the participants' name will be kept by the Principle Investigator in a secure place in a locked cabinet.

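### The primary SF-36 comparison is by default a completers' analysis: there is no rule for missing scores or deaths, and the 1-month SF-36 is never used, so it can be biased if loss relates to health differently by arm

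*Combined protocol and SAP*

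**What the plan says.** The Outcome Measures section defines the endpoint: "The primary outcome will be health status as measured with SF-36". The Data Analysis paragraph of that section gives the between-group method: "Post-trial data and change scores will be compared between the control and intervention groups using independent Student t tests and Mann-Whitney tests", the choice depending on normality. Within each arm, baseline is compared with post-study data only.

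The sample size paragraph under Patient Recruitment sizes the trial on the general health dimension, reaching 63 per group. It then raises this to 73: "Assuming 15% of patients will be lost to follow-up (including mortality".

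The Data Acquisition paragraph sets three questionnaire times: "Pre- and follow up questionnaires (baseline, 1-month, and 6-months), will be administered to both control and intervention groups". The 1-month form is handed out at enrolment, mailed back by the patient and prompted by a reminder call.

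The documents define no analysis population, no method for missing SF-36 scores, no rule for SF-36 after death, no sensitivity analysis and no use of the 1-month scores. Death appears among the secondary outcomes and in the loss allowance.

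**The concern.** A two-sample test on 6-month or change scores compares only those who reach 6 months and return the form. The patients are described in the Background as being at high risk of hospitalization and progression, the expected loss includes deaths, and only one arm uses the devices and app. Reasons for loss could therefore differ by arm. If they do, the remaining patients are no longer comparable, and an arm that loses more of its sickest patients can look healthier than it is.

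The plan collects scores that could reduce this risk and does not use them. It also names two comparisons without saying which is primary, and the two react differently to different kinds of loss.

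**Working it through.** **Inputs from the documents** (Patient Recruitment): target 10.5 points; control mean 57, SD 21; 80% power, two-sided alpha 0.05; 63 evaluable and 73 enrolled per group; 15% loss. **Assumptions:** correlations of 0.6 to 0.7 between visits, equal SDs, and every arm-specific loss pattern below.

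**1. The plan's own figure.** n = 2 × [21 × (1.960 + 0.842) / 10.5]² = 62.8, so 63 per group. Then 63 × 1.15 = 72.45, so 73 per group and 146 in all. Reproduced.

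**2. Who remains.** 146 × 0.15 = 21.9 patients have no 6-month score, and 73 × 0.85 = 62.05 per arm remain. Power is 79.5% (normal approximation) or 78.9% (t). The smaller number is not the problem; any problem lies in who is missing.

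**3. Bias in a completers' post-score comparison.** Let d be the share missing in an arm and D the completers' mean minus the missing patients' mean. Then bias = d_T × D_T − d_C × D_C. At 62 per arm the standard error is 21 × √(2/62) = 3.77.

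| Assumed loss, T / C | Assumed gap, T / C | Bias (points) | Type I error | Power if bias acts against the intervention |
|---|---|---|---|---|
| 15% / 15% | equal | 0 | 5% | 79.5% |
| 20% / 10% | 10.5 / 10.5 | 1.05 | 5.9% | 71% |
| 20% / 10% | 21 / 21 | 2.10 | 8.6% | 61% |
| 15% / 15% | 21 / 0 | 3.15 | 13.3% | 50% |

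**4. Which planned test is affected.** Write r01, r06 and r16 for the correlations between baseline, month 1 and month 6.

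- *Loss follows a low 1-month score.* If completers' mean 1-month score shifts by s, the post score shifts by r16 × s and the change score by (r16 − r01) × s. A post-score bias of 2.9 with r16 = 0.7 implies s = 2.9/0.7 = 4.1. With r01 = 0.6 the change score then moves by 0.1 × 4.1 = 0.4.
- *Loss follows decline from baseline to month 1.* The post score moves in proportion to r16 − r06, and the change score to 1 − r01 + r16 − r06. With r01 = r16 = 0.7 and r06 = 0.6 these are 0.1 and 0.4, so the change score is hit four times as hard.
- *Loss follows the 6-month state itself.* If the post score shifts by s, the change score shifts by (1 − r06) × s. A change-score bias of 1.7 with r06 = 0.6 corresponds to a post-score bias of 1.7/0.4 = 4.25.

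Simulations with no true effect (73 per arm, SD 21, about 14–18% outcome-related loss in one arm, 15% random loss in the other) agree:

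| Loss in one arm follows | Post score | Change score | Estimate using baseline and 1-month scores |
|---|---|---|---|
| Low 1-month score | about +2 to +3 | within about 0.7 of zero | about 0.0 |
| Early decline | near zero | about +1.5 to +2 | about 0.0 |
| 6-month state | about +4 (algebra above) | +1.4 to +1.9 | +2.2 to +2.9 |
| Same mechanism in both arms | about 0.0 | about 0.0 | 0 by symmetry |

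**5. Precision.** Using the 1-month score alone raises the effective number from 62 to about 63–67 per arm, and power from 79.5% to about 80–82%, if 50–100% of the missing patients returned the 1-month form and its correlation with month 6 is 0.5–0.7. Baseline adjustment contributes more: 3.77 × √(1 − 0.6²) = 3.02. In simulation the model's standard error was about 3.1, against 3.4–3.7 for the planned tests.

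**6. Deaths.** If deaths were scored 0, each 5-percentage-point difference in mortality would move the contrast by about 57 × 0.05 = 2.85 points. This measures how much the choice of death rule could matter; it is not an error in the planned test.

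**The case against.** The plan never says complete cases, and imputation before a t test is neither stated nor excluded. That is true. The completers' reading follows from the named tests, the absence of any missing-data rule and a sample size built to leave about 63 per group. It is the default, not a declared choice.

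A reader might infer that the primary result will be wrong by some 2.5 points, a quarter of the target. The documents do not support this. They give a single 15% figure, not split by arm, cause or timing, and no scores for missing patients. A figure of that size arises for the post-score test under one assumed one-arm mechanism, where the change score, which is also planned, is nearly unbiased. With the same mechanism in both arms, bias disappears.

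A reader might also infer that a repeated-measures model cures the problem. It gives 0.0 in the first two scenarios because loss there depends only on scores the model uses. When loss follows the 6-month state, it is biased by +2.2 or more and does somewhat worse than the change score. It treats deaths as if a later score existed, and it drops patients with no post-baseline score. Its benefit depends on patients mailing back the 1-month form.

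Finally, mortality and hospitalization-or-death are separate secondary outcomes, so a survival imbalance would be visible beside the SF-36. That helps interpretation but does not correct the primary contrast.

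These points limit the size of the claim and the reach of the remedy. They do not remove the gap: neither planned test is protected against both kinds of loss that observed scores could explain, and the scores needed are already collected.

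**Conclusion.** The point holds as a conditional one. By default the primary SF-36 comparison is a completers' analysis, and it can be biased if loss relates to health differently by arm. Illustrative sizes are about 2 to 3 points for the post score when loss follows a low 1-month score, and about 1.5 to 2 points for the change score when loss follows early decline. They rest on assumed correlations of 0.6–0.7 and outcome-related loss in one arm only. Bias is nil when loss acts alike in both arms.

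The documents do not show that differential loss will occur, that those lost will be sicker, or in which direction any bias would run. The change should be made because a better-protected analysis is available from data already planned, and because a rule fixed in advance prevents a later choice between two tests that may disagree.

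**What to change.** Make the primary analysis one likelihood-based repeated-measures model of SF-36 general health (the dimension used for the sample size) at 1 and 6 months. Include baseline score and the randomization strata as covariates, pooling sparse strata. Take the 6-month difference as the primary contrast, and include all randomized patients with any post-baseline score.

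State in the plan that the model assumes missing at random, and that it does not itself settle deaths or loss driven by unobserved late decline. Add two sensitivity analyses: one giving deaths the worst score, and one applying a delta adjustment to other losses. Report losses and deaths by arm.

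The cost is analysis wording, slightly more programming and two extra results to report; no new data, visits or patients are needed. The limits remain: the model removes bias only for loss explained by observed scores, and what it gains depends on return of the 1-month form.

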## Abstract

The rising prevalence of chronic illnesses threatens the sustainability of the healthcare system, especially due to the high cost of frequent hospitalizations. Effective self-management of chronic disease can reduce the need for urgent care but helping patients to master complex decision-making and to implement lifestyle changes is difficult. Telemonitoring systems are a promising adjunct in this regard. Such systems allow patients to monitor their physiological state (e.g. weight, blood pressure) and to receive both automated and real-time feedback from health care providers. Current systems tend to be inconvenient and costly to implement in existing clinical settings and are often limited to the monitoring of one chronic condition. We believe that delivering telemonitoring through a mobile phone will enable patients with complex chronic conditions to track their health, receive automated feedback relevant to their unique situations, and improve communication with their health care team in a cost effective and intuitive way.

In order to test the effectiveness of the intervention, we propose a 6-month randomized controlled trial of 146 patients. The study will include patients with a diagnosis of any of the following conditions or combinations of these conditions: heart failure, chronic obstructive pulmonary disease, chronic kidney disease, and/or uncontrolled hypertension. Insulin-requiring diabetes will be included as a co-morbidity to be supported by the telemonitoring application if the patient also has at least one of the four above chronic conditions. Patients will be assigned to either (1) the control group receiving usual care, or (2) the group using the mobile telemonitoring system in addition to usual care. We hypothesize that our mobile intervention will be a cost-effective and scalable tool that will improve health outcomes and quality of care, while empowering and reassuring patients and their family.

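### The planned net cost estimate has no stated between-arm mean difference per patient, no confidence interval and no link to effect, and the plan's only rule for non-normal data would not compare mean cost

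*Combined protocol and SAP*

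**What the plan says.** The Abstract states the hypothesis: "We hypothesize that our mobile intervention will be a cost-effective and scalable tool". Under Outcome Measures, cost is the first secondary outcome named: "outcome measure will be the cost (from the health system and patient perspectives"). Its components are listed: "The cost of healthcare will include hospitalizations, emergency department (ED) visits, clinic visits, delay of hemodialysis commencement, medications, and telemonitoring program". The EuroQol instrument appears in the same section only as a quality-of-life outcome: "general quality of life as measure by the EuroQol 5D-RL".

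The Data Acquisition paragraph says how resource use becomes money: "Standard cost values for a day in-hospital, ED visit, etc. will be used to estimate net cost savings or expenditures". It also says the cost of the intervention will be tracked, and it sets the questionnaire schedule: "Pre- and follow up questionnaires (baseline, 1-month, and 6-months), will be administered to both control and intervention groups".

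The Data Analysis paragraph gives one general rule for between-group comparisons: "Post-trial data and change scores will be compared between the control and intervention groups using independent Student t tests and Mann-Whitney tests", the choice depending on whether the data are normally distributed. The cost evaluation has its own sentences: "The cost evaluation will be performed by comparing any savings through reductions in hospitalization, emergency and clinic visits, through the use of the intervention", followed by amortised equipment, added clinical, technical and management resources, and indirect costs. Those sentences name no test, estimator or interval. The documents nowhere mention a bootstrap or other method for skewed costs, QALYs, a cost-effectiveness ratio or net benefit.

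**The concern.** A payer's budget depends on mean cost per patient. Patient-level costs are normally strongly skewed, because a minority with admissions account for most of the total. Two gaps follow.

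First, a net saving or expenditure reported without an interval cannot be told apart from chance when it rests on a handful of admissions in about 62 patients per arm.

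Second, an analyst who wants to test this secondary outcome finds only one stated rule, and for non-normal data it selects a rank test. Telemonitoring patients carry a programme cost, while the savings come from a few avoided admissions. Ranks register the small shift common to the whole arm and give little weight to the size of the rare large savings. The rank result and the mean difference can therefore have opposite signs.

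Separately, a cost-effectiveness hypothesis needs cost and effect considered together. Unless one arm is both cheaper and better, the plan as written has no means of answering it, although the EuroQol data are being collected. The Benefits to Society section looks to this trial for evidence on programmes that reduce healthcare costs, so the result is meant to be used.

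**Working it through.** **Plan figures.** No figure is given for the cost analysis. The only plan number used here is arm size. With a difference of 10.5, SD 21, 80% power and two-sided alpha 0.05:

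- n = 2 × (1.960 + 0.842)² × (21/10.5)² = 62.8, so 63 per group, as stated.
- 63 × 1.15 = 72.45, so 73 per group, as stated.
- Completers after 15% loss: 73 × 0.85 = 62 per arm.

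**Assumed inputs (none is in the documents).** Hospitalised: 30% control, 20% telemonitoring. Cost per hospitalised patient: exponential, mean 15,000. Non-hospital cost: lognormal, log-SD 0.8, mean varied from 500 to 4,000. Programme cost P for every telemonitoring patient: 300, 500 or 800.

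**True mean difference** (telemonitoring minus control) = P + (0.20 − 0.30) × 15,000 = P − 1,500. That is −1,200, −1,000 and −700, so telemonitoring is truly cheaper in every case below.

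**If Mann-Whitney is run on total cost,** the share of simulated trials that find telemonitoring significantly costlier (p < 0.05) is:

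| Mean non-hospital cost | P = 300 | P = 500 | P = 800 |
|---|---|---|---|
| 500 | 53% | 88% | 97% |
| 1,000 | 14% | 42% | 79% |
| 2,000 | 2% | 11% | 33% |
| 4,000 | 1% | 3% | 9% |

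A repeat with 2,000 trials per cell agrees to within 2 percentage points.

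**Other sensitivities.**

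- At mean 500 and P = 300, changing the log-SD from 0.5 to 1.0 moves the share from 76% to 48%.
- A different model (gamma routine cost with mean 1,000, lognormal hospital cost with mean 15,000, 63 per arm, 30% vs 20%) gives 0.1% with no programme cost, 6% at P = 250, 35% at 500 and 88% at 1,000.
- In the 500 row, trials in which the observed mean was lower with telemonitoring and Mann-Whitney still called it significantly costlier were about 30%, 56% and 62%. These shares are below 53%, 88% and 97% because the observed mean itself varies.

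**How wide the mean-difference interval would be (same assumptions).**

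- Variance of the hospital component = 2p × 15,000² − (p × 15,000)². This is 114.75 million for p = 0.3 and 81.00 million for p = 0.2.
- Non-hospital variance = mean² × (e^0.64 − 1) = 0.8965 × mean². This is 0.22 million at mean 500 and 14.3 million at mean 4,000.
- At mean 500: SE = √[(114.75 + 81.00 + 2 × 0.22) million / 62] ≈ 1,780, so the 95% half-width is 1.96 × 1,780 ≈ 3,490.
- At mean 4,000: SE = √[(195.75 + 28.7) million / 62] ≈ 1,900, so the half-width is about 3,730.

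A true saving of 1,000 would thus be reported with an interval of roughly ±3,500. A bare net figure hides this.

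**The case against.** The strongest defence is that the plan never says cost will be ranked. The Mann-Whitney sentence covers post-trial data and change scores in general, whereas cost has its own sentences, which describe adding up savings and netting off programme resources. With standard unit costs and 1:1 arms, that calculation expressed per patient amounts to a difference in arithmetic means. This stands. A reader might infer that the plan prescribes a rank test for cost, or that it has no mean cost comparison at all, and the documents support neither. The rank test reaches cost only by inference, and the reversal of sign concerns that test, not the planned net estimate.

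A second objection is that the high reversal rates depend on a low non-hospital cost. The plan also counts ED visits, medications and delayed hemodialysis, in complex patients, and at larger non-hospital costs the reversal becomes rare. This also stands: the mechanism is possible, but its frequency in this trial is unknown.

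A third is that cost per QALY is partly a matter of preference. Cost is one of many secondary outcomes, the trial is sized on the SF-36 alone, no cost-utility analysis is promised, and a six-month ratio would be very imprecise. Statisticians could reasonably differ, and a cost-consequence presentation could serve.

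None of these objections supplies the missing interval, names a per-patient estimator, or tells the analyst that the non-normal rule does not apply to cost.

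**Conclusion.** The point holds at limited scope. A net cost estimate is planned, but its per-patient between-arm estimator and its uncertainty are unspecified. The only stated rule for non-normal data would not compare mean cost if used on this outcome. No analysis joins cost to effect, despite the hypothesis in the Abstract and EuroQol scores in both arms at baseline, 1 and 6 months.

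The possible harm from ranking cost cannot be sized from the documents. Under the stated assumptions, the chance of calling telemonitoring significantly costlier when its true mean is lower runs from about 1% to 97%. A reader might take the upper end as the expected behaviour of the trial. That would be wrong, because it needs a mean non-hospital cost near 500, a programme cost near 800, and an analyst who applies Mann-Whitney to cost. The missing interval does not depend on those conditions. With about 62 per arm and these assumed costs, the 95% half-width is around 3,500 to 3,700, well above the assumed savings.

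This is a low-cost improvement to a secondary outcome. It does not affect the primary SF-36 analysis.

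**What to change.** In the Data Analysis paragraph, state that total cost per patient over 6 months, including programme cost, is compared as the difference in arithmetic means (telemonitoring minus control), with a bootstrap 95% confidence interval resampled within arm. State also that the t test/Mann-Whitney rule does not apply to cost.

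If the cost-effectiveness hypothesis is kept, report the mean cost difference jointly with the EuroQol-based effect as an exploratory analysis. QALYs from the three questionnaire time points, with net benefit or a cost-effectiveness plane, would do this. Otherwise limit the claim to cost.

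The change needs wording and some programming, with no new data collection or patients. Its price is an interval that will be wide and should be reported as such.
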